### **Arrangement of participants**

Summaries of the number of randomized patients, number of those completing the study, and incidence of protocol violations will be provided for each treatment group. The number (%) of participants with protocol violations that may affect study objectives will be based on database analysis. This evaluation will be done before determining the allocation of treatment for all participants in the database.

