A recent study comparing mortality rates between low-income and high-income countries in participants with AIDS starting ARV therapy demonstrated that the risk ratio for early death was 4.3 times higher (95% CI: 1.6 - 11 .8), in poorer countries, but dropped to 1.5 after seven months of therapy (6). Furthermore, another report comparing mortality rates among participants with AIDS in Brazil and the USA showed that individuals with CD4+ cell counts below 50 cells/mm³ had a 4.8 times greater risk of death after starting ART and the proportion of early deaths in the first three months was significantly higher for Brazilian participants compared to Americans (14).

In Brazil and other developing countries, there is still a large proportion of participants with AIDS who are diagnosed with AIDS, or who only seek health care for HIV infection in the final course of the illness. While a median first CD4+ cell count below 200 is a frequent finding for most countries in the world, it is expected to be even lower for participants living in resource-limited countries, making the problem of early mortality an issue. important concern.

Dolutegravir (DTG), an HIV-1 integrase inhibitor, is a potent and safe antiretroviral drug (14). Available evidence suggests that drugs in this class promote a more rapid reduction in HIV-1 plasma viremia, and a greater increase in CD4+ cell count, compared to EFV (15,16).

We propose to compare the impact of DTG versus EFV on early mortality rates in critically ill participants starting antiretroviral therapy (CD4+ <50 cells/mm³).

4. Study Design

This is a pilot, open-label study to prospectively assess the rate of early all-cause mortality in participants initiating ART with DTG-based regimens. Retrospectively, the medical records of participants who used EFV in the years 2014-2016 will be reviewed for comparison purposes.

5. Local

The study will be conducted by FBaI - Fundação Bahiana de Infectologia (Bahia) - Investigator: [name], and will include 4 additional sites in different Brazilian cities (Manaus, Natal, Florianópolis, and Porto Alegre)

6. Sample size

The total number of participants included in each study arm will be 92. The calculation of this sample size is detailed in the SAMPLE SIZE section.

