12.1. Sample Size Justification

Mortality rates are quite variable, depending on region, specific study, and population.

Most studies from African countries have shown that mortality in the first 3 months of ART for participants with CD4+ cells under the threshold of 50 cells/mm³ is generally greater than 30%, and may reach 52% in some reports.

On the other hand, in developed countries, most deaths in such a population usually occur after 7 months of therapy and the mortality rate is just as low (1.8% for the first year of treatment).

We estimated that early mortality for participants included in the EFV arm would be similar to the rates detected in African countries (around 30%). We hypothesize that participants using DTG-based regimens would benefit from faster recovery of CD4+ cell count and that they behave like those individuals starting antiretroviral therapy in developed countries (mortality rate around 2%).

Considering a lower limit of 2% (DTG arm) and an upper limit of 25% (EFV arm), a 95% CI and 80% power to detect differences between groups, it would be necessary to treat a total of 84 participants (42 on each arm). Adding 10% for dropouts, this would result in a total of 92 subjects (46 in each arm).

With the recent changes in treatment recommendations, all 92 participants will receive DTG. Participants who used EFV will be retrospectively evaluated, through the review of medical records, in an identical number (92 participants).

This will be an exploratory pilot study.

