## **Statistical Analysis Plan**

### **General Considerations**

All abstracts and statistical analyzes will be provided for the intended **intention to treat population**, defined as all participants who are randomized to treatment. With the exception of the Primary Efficacy Parameter Analysis, percentage of responders for the intent-to-treat population, missing data will not be estimated or transported in any statistical analyzes.

All comparisons of treatment groups will be performed using two-tailed tests at a significance level of 0.05 ( $p < 0.05$ ). The null hypothesis for all analyzes is that there is no difference between the treatment groups.

All abstracts, statistical analyzes and individual record data of participants described below will be provided in separate annexes. Separate listings will be provided for each of the treatment groups in the intention-to-treat population.

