### **Demographic Characteristics and Disease**

The statistical analyzes described below will be completed to:

- The population of intention to treat participant;
- The evaluable population of effectiveness.

Demographic Characteristics

The table below identifies the demographic and disease characteristics used to determine the comparability of treatment groups and the methods used to analyze them.

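### The intention-to-treat set and the pre-allocation violation review presuppose a randomised, masked trial; neither works here, and little else in the plan keeps inclusion decisions blind to outcome

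*SAP*

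**What the plan says.** The SAP (General Considerations) makes the intention-to-treat population the basis of all analyses, "defined as all participants who are randomized to treatment". Under Arrangement of participants it promises a count of randomised patients per group. It then adds: "The number (%) of participants with protocol violations that may affect study objectives will be based on database analysis". The next sentence sets the timing: "This evaluation will be done before determining the allocation of treatment for all participants in the database". Protocol sections 12.3 and 12.4 carry the same rules.

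Under Demographic Characteristics and Disease, the SAP lists a second population for the analyses, "The evaluable population of effectiveness". Neither document defines it.

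The design is different. Protocol section 4 describes an open-label study in which "the medical records of participants who used EFV in the years 2014-2016 will be reviewed for comparison purposes". Section 12.1 says that, after a change in treatment recommendations, "all 92 participants will receive DTG", with an equal number of EFV participants taken from records. Section 11 asks for eligible participants to be taken consecutively up to the target number. Section 8.1 excludes from the retrospective group those who were asymptomatic when ART began, without defining the term.

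**The concern.** Who is analysed has to be settled by rules that do not depend on how the participant fared. A randomised, masked trial gets this from two things: the randomised set is fixed at entry, and violations are classified before the code is broken. This plan borrows both, and neither carries over to a prospective DTG cohort compared with historical EFV charts.

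For the charts, who counts as included is exactly what needs a rule. EFV use dates from 2014–2016 (section 4) or 2013–2016 (section 7.1), so one-year survival may already be on the page when eligibility is judged. For both groups, the evaluable set could be settled after outcomes are known. Deaths may be few, so a small number of such decisions could shift the mortality comparison.

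**Working it through.** **1. Set the rules beside the design.**

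| SAP rule | What the design offers |
|---|---|
| Population is those randomised | No randomisation. All 92 prospective participants get DTG and 92 EFV records are reviewed (Protocol 12.1). The allocation number in 10.3 is only a chronological identifier. |
| Violations judged before treatment allocation is determined | Open-label (Protocol 4). Group follows from data source. It also shows in the visit schedule (10.1 against 10.2) and in the eligibility lists (7.1 against 7.2). |
| Violations counted per group | No list of violations, and no statement of what follows from one. |
| Evaluable population | Named, not defined. |

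Read literally, 0 of 92 + 92 = 184 participants belong to the intention-to-treat set.

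**2. Which safeguards remain?** Section 11 requires consecutive selection. Most chart criteria in 7.1 are objective: CD4+ count, viral load, age, confirmed infection, EFV as first therapy. The asymptomatic exclusion needs judgement. No masking of the assessor to outcome is described.

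**3. The plan's own figure.** The concern does not touch the sample size, but it was checked. Inputs from Protocol 12.1 and 12.3: 25% and 2%, 80% power, two-sided 0.05. Mean proportion = (0.25 + 0.02)/2 = 0.135.

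- Uncorrected: n = [1.96·√(2·0.135·0.865) + 0.842·√(0.25·0.75 + 0.02·0.98)]² / 0.23² = 33.4, so 34.
- Continuity-corrected: n′ = (33.4/4)·[1 + √(1 + 4/(33.4·0.23))]² = 41.7, so 42 per arm, as the Protocol states.

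**4. How sensitive is the mortality comparison?** The documents give no death counts, so all counts here are assumptions. Test: chi-square without continuity correction, X² = N(ad − bc)² / (product of the four margins), with a, b the EFV deaths and survivors and c, d the DTG deaths and survivors.

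- *Start:* 14/92 EFV, 6/92 DTG. X² = 184·(14·86 − 78·6)² / (92·92·20·164) = 3.59, p = 0.058.
- *Chart route:* one EFV survivor is judged asymptomatic and the next consecutive chart is a death, giving 15/92 against 6/92. X² = 184·(15·86 − 77·6)² / (92·92·21·163) = 4.35, p = 0.037.
- *Evaluable-set route:* one DTG death is left out, giving 14/92 against 5/91. X² = 183·(14·86 − 78·5)² / (92·91·19·164) = 4.65, p = 0.031.

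Other starting points, evaluable-set route:

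| EFV deaths | DTG deaths | p | DTG deaths left out to reach p < 0.05 |
|---|---|---|---|
| 23 | 13 | 0.063 | 1 (p = 0.042) |
| 14 | 8 | 0.173 | 3 (p = 0.035) |
| 9 | 9 | 1.00 | 7 (p = 0.041) |
| 14 | 14 | 1.00 | 10 (p = 0.025) |
| 23 | 23 | 1.00 | 13 (p = 0.041) |

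**5. False-positive risk under equal true mortality.** Assume 92 per group, true mortality 15% to 25%, and each DTG death left out with probability f. Binomial enumeration gives:

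| f | Two-sided false-positive risk |
|---|---|
| 0 | 4.9–5.1% |
| 10% | 5.8–6.1% |
| 20% | 8.1–9.6% |
| 30% | 12.4–16.3% |

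**The case against.** The strongest reply is that this is leftover wording with no stated consequence. The SAP counts violations and removes nobody, and neither document links violations to the evaluable set. A reader might infer that exclusions will be made with group and outcome visible. The documents do not support that: they are silent on exclusion, so the most that can be said is that nothing prevents it. A reader might also infer that the pre-allocation review is the only protection. It is not, because consecutive selection bears directly on picking charts by outcome, and most chart criteria are objective.

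Three further points have force. Any analyst would read the main set as those enrolled on DTG plus those selected on EFV, so the count of 0 of 184 shows a misfit and does not measure bias. DTG eligibility is settled at entry, before outcomes exist, so losing DTG deaths would need a later removal that no text describes. And single-record effects appear only when the result already sits near 0.05; a difference is not easily created from equal counts.

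What remains is narrower. Consecutive order does not say how eligibility is judged, or who is later non-evaluable. The obvious reading of the main set does not say whether an EFV chart with missing week 24 or 48 data counts. Calling the study an exploratory pilot does not settle this while the plan still specifies two-sided 0.05 tests between groups.

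**Conclusion.** The point holds in limited form. The randomised set does not apply and the pre-allocation review is unworkable; both follow from the documents alone. Apart from consecutive selection, the plan leaves chart eligibility under the asymptomatic criterion, and membership of the evaluable set, open to decision with group and outcome known. It does not follow that such decisions will be made, or that violators will be dropped.

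The size cannot be taken from the documents. On the assumed counts, one record matters when p is about 0.06, and 7 to 13 DTG deaths would have to be left out if counts start equal. If a fifth of DTG deaths were left out under equal true mortality of 15% to 25%, the false-positive risk would rise from about 5% to 8–10%. The plan should be corrected before chart outcomes are extracted. The sample size is unaffected.

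**What to change.** - **Main population.** Define it as all eligible participants who started DTG (prospective) or EFV (charts), analysed by starting drug, with no exclusions after the start of therapy. Drop the references to randomised patients in the SAP and in Protocol 12.3 and 12.4.
- **Evaluable set.** Delete it, or define it by criteria that are fixed before data extraction and do not depend on outcome.
- **Allocation sentence.** Replace it with: EFV charts are screened consecutively by ART start date; eligibility is recorded and locked from baseline fields before outcome fields are abstracted; every excluded record is logged with its reason.
- **Violations.** Keep the summary of on-study violations by group, and state that a violation removes nobody from the main analysis.
- **Eligibility wording.** State how asymptomatic is to be judged from a chart, and reconcile the two EFV year ranges (Protocol 4 and 7.1).

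The cost is SAP and Protocol wording, a two-step abstraction form and a screening log. An abstractor holding the full chart may still glimpse the outcome, so the lock reduces this bias without removing it. Withholding outcomes fully would need a second person or a prepared extract.

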### **Demographic Characteristics and Disease**

The statistical analyzes described below will be completed to:

- The population of intention to treat participant;
- The evaluable population of effectiveness.

Demographic Characteristics

The table below identifies the demographic and disease characteristics used to determine the comparability of treatment groups and the methods used to analyze them.

**Table 1 - Variables analyzed to determine comparability**

Variable	Analysis method
Basal age	One-way ANOVA/KW
Basal VL	One-way ANOVA/KW
CD4 + basal	One-way ANOVA/KW

The primary efficacy endpoint is the number (%) of participants who achieved the primary endpoint (HIV-1 Viral Load RNA <50 copies / ml) at week 48 (or discontinuation) visit. Participants will be counted as non-responders if they do not attend Week 48 (or term).

The DTG treatment group will be compared to the EFV group with respect to the percentage of responders using a chi-square test. Two-tailed, 95% confidence intervals for the percentage of responders will be calculated for each treatment group.

The following table identifies the secondary endpoints of effectiveness and the methods used to analyze them.

**Table 2 - Variables analyzed in the main points of analysis**

Variable	Analysis method
Frequency of Adverse Events	chi-square test
Proportion of participants achieving VL <50 copies / ml at each point of analysis	chi-square test
Proportion of deaths	chi-square test

CD4 + count at each point of analysis	One-way ANOVA/KW
---------------------------------------	------------------

### **Security Endpoints**

Summaries and statistical analyzes of safety parameters will be completed for the population by intention to treat. The incidence of at least one grade III or IV event will be the primary safety objective of the study. Treatment groups will be compared to the percentage of participants with at least one grade III or IV adverse event using a Chi-square test.

### **Serious Adverse Events**

Secondary safety endpoints are the incidence of adverse events classified according to the preferred term and body system, the results of clinically significant laboratory tests and changes in vital signs. Treatment groups will be compared with the percentage of participants with clinically significant laboratory test results at Week 4, 8, 16, 24, 36 or 48 visits using Chi-square.

Summaries of physical examination data, vital signs (actual value and baseline change) and laboratory data (real value and change of baseline) will be provided at each visit.

### **Report of Adverse Experiences**

The investigator and local staff will be responsible for documenting, detecting and reporting events that correspond to the definition of Adverse Event, which is defined as any undesired medical event occurring in a participant or individual involved in a clinical investigation protocol, which may be transiently associated with the use of a medical product, whether or not it is considered to be related to the test product. A serious adverse event (SAE) is defined as any medical event that results in death or life-threatening, hospitalization, disability, congenital anomaly, or all grade 3 or higher liver damage caused by drugs.
